## The immunological basis for treatment resistance to anti-TNF treatments

### Rationale and Hypothesis

Anti-TNF treatments such as etanercept are one of the most effective treatments available for psoriasis, but treatment response can vary substantially and a subgroup of patients may show minimal or no response even at high doses, despite having otherwise identical clinical features. The biologic basis for the resistance to anti-TNF treatment is unknown but several separate lines of evidence indicate that it might be due to cross-regulation between tumor necrosis factor (TNF)- $\alpha$  and the type I interferon (IFN), IFN- $\alpha$ .

The major source of type I IFNs are plasmacytoid dendritic cells (pDCs). pDCs are rare in healthy skin but are often increased in psoriatic skin (4) and have been implicated in the pathogenesis of psoriasis, particularly in triggering plaque development, which has been shown to be dependent on IFN- $\alpha$  production in a xenograft mouse model. Type I IFNs inhibit TNF- $\alpha$  production from monocyte-derived inflammatory cells and anti-TNF pretreated pDCs have about a three-fold increase in IFN- $\alpha$  production. Furthermore, TNF blockade is consistently associated with an increased IFN- $\alpha$  signature in blood cells. In stark contrast, and consistent with the cross-regulation between these two cytokines, TNF- $\alpha$  inhibits the release of IFN- $\alpha$  from pDCs as well as generation of pDCs from hematopoietic precursors.

The clinical evidence supporting this phenomenon has grown over the past few years. The induction or exacerbation of psoriasis during anti-TNF therapy, which has now been reported in several hundred patients (9, 10) is one such example, and may occur in patients treated for inflammatory conditions other than psoriasis. The psoriatic lesions of these patients have a greatly increased type I interferon signal, as determined by increased tell-tale Myxovirus Resistance Gene A (MxA) expression, compared with control psoriasis samples and similar observations have been made in patients exposed to the Toll-like receptor (TLR)-7 agonist imiquimod. Imiquimod is a very effective inducer of type I interferon production by pDCs (15) and has been shown to exacerbate psoriasis both at the treated area as well as distant skin sites. Similarly, to anti-TNF exacerbated psoriasis, this reaction is accompanied by influx of pDCs and increased MxA expression. Interestingly, but in line with the observations above, this reaction appears to be exacerbated in patients on anti-TNF treatment. This cross-regulation is likely to extend beyond psoriasis as diseases characterized by increased type I IFN signal are frequently exacerbated or triggered by TNF treatments, including lichenoid skin reactions and the increased frequency of positive anti-double stranded DNA antibody titers and less commonly clinical systemic lupus erythematosus, which are both reversible upon discontinuation of treatment.

We have demonstrated that the inflammatory and cytokine network in chronic plaque psoriasis is heterogenous with large variation in the strength of the type I

IFN- $\alpha$  and TNF- $\alpha$  signals between different patients. Thus, about 35-40% of patients show an enriched IFN- $\alpha$  signature in lesional psoriatic skin, which, perhaps coincidentally, is around the same ratio of patients showing limited response to etanercept therapy. Our analysis of a small cohort of patients (n=15) treated with etanercept indicated that those patients with increased IFN- $\alpha$  signal had poorer response to therapy and that the strength of the IFN- $\alpha$  signal was the main predictor of treatment response.

These observations form the basis of our hypothesis **that the balance between type I IFN and TNF determines the response to anti-TNF treatment**. The goal of the proposed study is to address this hypothesis and demonstrate that the strength of the type I IFN signature in psoriatic skin is the major determinant of the clinical response to anti-TNF treatment.

### Proposed experiments

Purpose: Determine the strength of the type I interferon and TNF signal in psoriatic skin prior to and during treatment with etanercept and correlate with degree of clinical improvement.

Psoriatic patients will receive 100 mg etanercept per week (2 separate single-use pre-filled 50 mg subcutaneous injections taken on two separate days) for 3 months. Inclusion and exclusion criteria will be identical to the previous EASE trial (with the exception of the highlighted items), as follows:

#### **Inclusion:**

1. At least 18 years of age at screening.
2. Clinically stable moderate to severe plaque psoriasis at screening and baseline.
3. Subject must be:
  - A man **or**
  - A woman who is surgically sterile or at least 3 years postmenopausal **or**
  - A woman of childbearing potential who has had a negative pregnancy test within 7 days before the first dose of study drug.
4. If the subject is sexually active, (s)he must agree to use a medically acceptable form of contraception during screening and throughout the study.

#### **Exclusion:**

1. Grade 3 or 4 adverse events or infections within 28 days before screening, or between the screening visit and drug initiation.
2. Active or chronic infection within 4 weeks before screening visit, or between the screening and baseline visits.
3. Evidence of skin conditions other than psoriasis that would interfere with the evaluations of the effect of study medication on psoriasis.

4. Use of oral psoralen with ultraviolet A (PUVA), oral retinoids, cyclosporine, alefacept, or any other systemic anti-psoriasis therapy within 28 days of study drug initiation.
5. Use of ultraviolet B (UVB) therapy, topical steroids at no higher than moderate strength, topical vitamin A or D analog preparations, or anthralin with 14 days of study initiation.
6. Prior or concurrent use of cyclophosphamide therapy
7. Concurrent sulfasalazine therapy.
8. Known hypersensitivity to Enbrel® (etanercept) or any of its components or known to have antibodies to etanercept.
9. Current enrollment in any other investigational device or investigational drug trial(s), or receipt of any other investigational agent(s) within 28 days before baseline visit.
10. Use of any biologic drugs within 28 days of study drug initiation.
11. Concurrent use of Anakinra.
12. Severe comorbidities (diabetes mellitus requiring insulin; congestive heart failure (CHF) of any severity or myocardial infarction or cerebrovascular accident or transient ischemic attack within 3 months of screening visit; unstable angina pectoris, uncontrolled hypertension (sitting systolic BP <80 mm Hg or > 160 or diastolic BP > 100 mm Hg), oxygen-dependent severe pulmonary disease, history of cancer within 5 years (other than resected cutaneous basal or squamous cell carcinoma of the skin or in situ cervical cancer)
13. Known history of tuberculosis (TB), or previous positive purified protein derivative (PPD) test. Any mycobacterial disease or high risk factors for tuberculosis (TB), such as family member with TB, positive purified protein derivative (PPD) or taking anti-tuberculosis medication.
14. Known HIV-positive status or known history of any other immuno-suppressing disease.
15. Concurrent or history of psychiatric disease that would interfere with ability to comply with study protocol or give informed consent.
16. History of alcohol or drug abuse within 12 months of screening visit.
17. Latex sensitivity [Nota Bene: only applicable if they are using prefilled syringe or prefilled SureClick™ autoinjector presentations]
18. Exposure to hepatitis B or hepatitis C or to high risk factors for hepatitis B or C, such as intravenous drug use in patient.
19. Systemic lupus erythematosus, history of multiple sclerosis, transverse myelitis, optic neuritis or seizure disorder.
20. Use of a live vaccine 90 days prior to screening visit, or concurrent use of a live vaccine.
21. Any condition or circumstances judged by the patient's physician[or the investigator or medically qualified study staff] to render this clinical trial detrimental or otherwise unsuitable for the patient's participation.
22. History of non-compliance with other therapies.
23. Pregnant or nursing females.

24. Diagnosis of multiple sclerosis in first degree family relationship (parent, sibling or child)

Flow Chart of visits:

Visits	Screening	BL	Week2	Week 6	Week 12
ICF	X				
Med/Hx	X				
Con Meds	X	X	X	X	X
Biopsies		X	X	X	X
Inc/exc	X				
Screening labs (CBC, metabolic panel)	X				
TB Test*	X				
Blood		X	X	X	X
Dispense Drug		X	X	X	
Urine Pregnancy Test	X	X		X	
Photos		X	X	X	X
Injection Instruction		X			
Physical Exam	X	X			
PASI/PGA/BSA/ Itch Assessment**	X	X	X	X	X

\*Subjects will be tested for TB at the screening visit and will return to research clinic 2 days later so that the area can be examined and the result documented.

\*\*Subjects will be asked to verbally indicate their level of itch on a scale of 0 to 10 at each visit.

Adverse events will be reported in accordance with the guidelines of the Institutional Review Board (IRB) and the Food and Drug Administration (FDA). Concomitant medications will be recorded. All serious adverse events, regardless of causation, will be reported to the IRB and Amgen Global Safety (see below) within one working day. All serious and medically significant adverse events considered related to etanercept by the investigator will be followed until resolved or considered stable. Unexpected and fatal or life-threatening events will be reported to the FDA by phone or FAX within 7 calendar days. Written reports will be sent to the FDA within 15 calendar days for any serious unexpected adverse events for which there is reasonable possibility that the event may have been caused by the study drug. Any pregnancies occurring on study must also be reported to Amgen Global Safety (see below). Within 24 hours of FDA notification, a copy of all FDA submitted reports will be sent to Amgen by facsimile or mail at the following address:

Amgen Global Safety  
c/o Amgen  
[name]  
[name]  
*[name]*  
*[contact]*

At the screening visit, subjects will have a TB test performed, as well as skin exams, physical exams, medical history review, etc. as documented in the study flow sheet to determine if they meet the entrance requirements.

Peripheral blood and biopsies will be obtained from 50 psoriatic patients with active lesions, who have not received any systemic treatment for four weeks, or any topical treatment other than bland emollients for two weeks. Peripheral blood mononuclear cells (PBMC) will be isolated from blood (approximately 4-6 tubes) taken from psoriatic patients prior to treatment and at every visit of etanercept treatment (see flow chart). The isolated PBMCs will be cryopreserved and stored in liquid nitrogen, or used immediately for experiments. Serum will be stored for future cytokine measurements and levels of anti-nuclear antibodies (ANA) by ELISAs. Cellular staining will be determined by twelve-color BD LSR II flow-cytometer. Two biopsies will be taken at baseline (uninvolved and lesional psoriatic skin) and at each visit (lesional only) at week 2, 6 and 12. Gene and protein expression may be analyzed in whole-biopsies, or certain cell populations may be isolated from biopsies to perform flow cytometry, gene expression studies, protein expression studies, and other laboratory studies.

1. Demonstrate that the strength of type I IFN signature in psoriatic skin predicts treatment response.

Fifty individuals with moderate to severe psoriasis with high dose etanercept (50mg twice weekly), and the composition of the lesional psoriatic cytokine network will be tracked at the onset (day 0), early (week 2), during the middle (week 6) and at the end of treatment (week 12). Serum samples and PBMC isolation will be done at each time-point for later analyses. Biopsies of uninvolved and lesional skin will be performed before initiation of treatment and then lesional biopsies taken at week 2, week 6 and week 12. Skin will be anaesthetized with 1% lidocaine with epinephrine and 6mm punch biopsies will be taken. Photographs of patients will be obtained and the anatomical location of biopsies recorded. Biopsies will be bisected, with one-half snap frozen in liquid nitrogen and stored at -80° until RNA and protein processing and the other half fixed in 4% formalin for paraffin embedding and immunohistochemistry. Processing will be performed as previously described by our team and only high quality RNA, as determined by Agilent 2100 Bioanalyzer will be used .

Next-generation sequencing of RNA (RNAseq) will be performed on the samples according to Illumina's protocol using 2 $\mu$ g of RNA. Immunohistochemistry will be performed to validate findings with MXA staining used to confirm presence of type I interferon signal. H&E staining will be used to assess the degree of epidermal hyperplasia and response to treatment and immunohistochemical detection of keratin 16, CD3, CD11c, CD163, Ki67 used to validate the degree of histologic response in context of the clinical response. QRT-PCR will be performed for selected gene transcripts to validate the findings of RNAseq.

**Analysis/Statistics:** RNAseq reads will be mapped using the TopHat algorithm and gene expression levels will be expressed as reads per kilobase of region per million mapped reads (RPKM). Based on prior experience, we estimate that we will obtain around 3 gigabases of sequence for each sample. Inflammation profiles and cytokine signature scores will be calculated as described by our group. Estimating that around 50% of patients will achieve a 75% reduction in Psoriasis Area and Severity Index (PASI) (PASI75) at 12 weeks; this should allow us to determine if effective treatment is associated with complete neutralization of the TNF signal in lesional psoriatic skin and elucidate the effect of the strength of the type I IFN signal on treatment response. For our statistical analyses, we are interested in one outcome variable (PASI score) and two continuous covariates (RNAseq-generated TNF- $\alpha$  signal and IFN- $\alpha$  signal). We anticipate that these data will be analyzed in two ways.

(1) First, we will test whether temporal change in PASI score is significantly associated with baseline TNF- $\alpha$  signal, baseline IFN- $\alpha$  signal, and/or an interaction between these two baseline signals. Along these lines, a cumulative score reflecting change in PASI during the course of etanercept treatment will be calculated for each patient. This score will then be treated as a continuous response variable, and we will use robust linear modeling to test whether scores are significantly associated with baseline TNF- $\alpha$  signal, baseline IFN- $\alpha$  signal, and/or an interaction between these two signals. In addition, we expect that it will be possible to unambiguously classify 30% of patients as non-responders, with an equal percentage showing clear improvement in PASI score, and the remainder showing an intermediate response. Accordingly, we will also categorize patients according to improvement in PASI score (i.e., responders, intermediate-responders, and non-responders), and use cross-validation to calculate AUC statistics to directly quantify the capacity of baseline TNF- $\alpha$  and IFN- $\alpha$  signals to predict patient response status. Based upon preliminary data ( $n$  = 15 patients), we anticipate that improved PASI score will be associated with a heightened baseline TNF- $\alpha$  signal and weakened baseline IFN- $\alpha$  signal. The proposed study design will allow us to not only confirm this expectation, but will provide increased power to assess a possible TNF- $\alpha$ /IFN- $\alpha$  interaction effect, and to better characterize quantitative thresholds associated with response and non-response.

(2) Second, we will test whether TNF- $\alpha$  and/or IFN- $\alpha$  signals are significantly altered during the course of etanercept therapy, and whether such changes differ between subjects with different PASI response profiles. In these analyses, TNF- $\alpha$  or IFN- $\alpha$  signal will be treated as a response variable in a univariate repeated measures analysis of variance, with subject and time as covariates. In this framework, a shift in TNF- $\alpha$  or IFN- $\alpha$  signal during the course of etanercept treatment will be indicated by a significant time effect. In follow-up analyses, models will include 0-1 covariates indicating specific PASI response profiles (e.g., non-responder, intermediate-responder, or responder), which will allow us to test whether temporal shifts in TNF- $\alpha$  or IFN- $\alpha$  signals differ according to the effectiveness of etanercept treatment (i.e., by evaluating interaction effects involving time and 0-1 covariates denoting PASI response patterns). We anticipate that etanercept treatment will more strongly attenuate TNF- $\alpha$  signals in responders compared to intermediate-responders or non-responders (possibly due to disparities in baseline TNF- $\alpha$  and IFN- $\alpha$  signals). Conversely, we expect that non-responders will be characterized by high IFN- $\alpha$  signals, which remain high during the course of etanercept treatment. All analyses performed using PASI scores will be repeated using physician global assessment scores as the response variable, although we expect results from these two analyses to be consistent. With 50 patients recruited and treated, we estimate that we will have >95% statistical power to detect significant effects in the proposed design (Type I error rate of 0.05). Although the analysis will be primarily focused on TNF and IFN signatures, this dataset will also provide us with opportunities to determine contribution of other inflammatory cellular and cytokine contribution to the clinical response.

**Anticipated Results:** We expect that patients with strong IFN- $\alpha$  signature in psoriatic skin along with weak TNF- $\alpha$  signature will have minimal response to anti-TNF treatment, while patients with the opposite pattern, weak IFN and strong TNF signature, will have significant clinical improvement.

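### Exclusion 5 bars mild and moderate topical steroids but not potent ones, and omits unnamed active topicals, contradicting the protocol's own two-week bland-emollient washout

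*Combined protocol and SAP*

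**What the plan says.** The section Proposed experiments introduces the numbered list as the trial's eligibility criteria: "Inclusion and exclusion criteria will be identical to the previous EASE trial (with the exception of the highlighted items), as follows". Within that list, Exclusion item 5 covers recent UVB and topical therapy. After UVB it names "topical steroids at no higher than moderate strength, topical vitamin A or D analog preparations, or anthralin with 14 days of study initiation".

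A second rule stands outside the list, in the paragraph on blood and biopsy collection that follows the flow chart and the adverse-event reporting text. It says that samples come from 50 patients with active lesions who have had no systemic treatment for four weeks, "or any topical treatment other than bland emollients for two weeks".

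The numbered item on predicting treatment response then states "Biopsies of uninvolved and lesional skin will be performed before initiation of treatment". In part (1) of Analysis/Statistics the signals measured at baseline become the predictors: "we will use robust linear modeling to test whether scores are significantly associated with baseline" TNF-α signal, IFN-α signal and their interaction. The same two signals feed the cross-validated AUC for response status.

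**The concern.** In an exclusion list, a strength limit set as a ceiling works backwards. It removes the patients whose topical steroid was weaker and leaves in those whose steroid was stronger. The item also works by naming classes and has no closing clause for other topicals, so an active product outside those classes is not caught.

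At stake is whether baseline lesional skin is free of recent active topical treatment when it is biopsied. The goal of the study is to show that the strength of the type I IFN signature in psoriatic skin determines clinical response, so the baseline biopsy is the key measurement. The sponsor's own two-week washout shows that it wants that tissue free of active topicals. A patient who meets every numbered criterion can still be one whom the collection paragraph rules out.

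**Working it through.** No arithmetic beyond counting applies, and the plan gives no figure on this point to reproduce. The check compares the two rules.

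**Step 1. Does any other numbered criterion cover topicals?** There are 4 inclusion and 24 exclusion criteria, 4 + 24 = 28. The candidates are:

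- Exclusion 3 concerns skin conditions other than psoriasis.
- Exclusion 4 has a catch-all clause, but for systemic therapy only (28 days).
- Exclusion 10 concerns biologics.
- Exclusion 21 lets a physician or the investigator exclude a patient by judgement. It mentions neither topicals nor a washout.

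That leaves item 5 as the only criterion that sets a topical rule: 1 of 28.

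**Step 2. Apply both rules to each kind of topical used in the last 14 days, reading item 5 literally.**

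| Topical used in the last 14 days | Exclusion 5 | Collection paragraph | Agree? |
|---|---|---|---|
| Mild or moderate steroid | excluded | barred | yes |
| Potent steroid | not excluded | barred | **no** |
| Active topical of a class not named in item 5 | not excluded | barred | **no** |
| Vitamin A or D analog, or anthralin | excluded | barred | yes |
| Bland emollient | allowed | allowed | yes |

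The rules disagree in 2 of 5 categories. In both, the numbered list is the looser rule. These are categories of treatment, not proportions of patients.

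**Step 3. Does the result depend on the literal reading?** Suppose, as an assumption, that a word such as 'except' was lost, so that steroids up to moderate strength were meant to be allowed and stronger ones barred. The first row then becomes a disagreement and the second an agreement. The third is unchanged. The count is again 2 of 5, so item 5 would need correcting on that reading too.

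**Step 4. Timing.** Item 5 counts 14 days from study initiation, whereas items 4 and 10 count from initiation of study drug. The word before '14 days' also appears to be a slip for 'within'. The collection paragraph's two weeks is the same length, so the conflict concerns which products are covered and not how long the washout lasts.

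**The case against.** The strongest reply is that the protocol already contains the right rule. The collection paragraph applies to all 50 planned patients, and the two rules are compatible, since following the broader one satisfies both. Concomitant medications are reviewed at screening and again at baseline, so topical use should come to light before etanercept starts. Exclusion 21 also allows such a patient to be turned away. Nothing says that eligibility is judged from the numbered list alone. The paragraph before the washout rule says that screening procedures are done "as documented in the study flow sheet to determine if they meet the entrance requirements", and those requirements could be taken to include the washout.

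Much of this stands. It means that the protocol does not lack a washout, and that an ineligible patient would be biopsied only if staff worked from the list without the collection paragraph. It does not remove the contradiction. The bland-emollient rule is not in the list that the protocol presents as its inclusion and exclusion criteria. A medication review may reveal a potent steroid, but item 5 as worded gives no ground to exclude for it, and item 21 is discretionary.

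The list is also said to follow an earlier trial apart from highlighted items. The highlighting is not visible in the text reviewed and the earlier criteria are not available, so the intention behind item 5 cannot be established. Highlighting would not change what the words say.

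**Conclusion.** Exclusion 5 is wrong as written and contradicts the washout stated elsewhere in the same protocol. It should be corrected. The conclusion rests on the wording alone: one criterion of 28 deals with topicals, and it leaves two categories of recent topical use open that the collection paragraph closes.

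Three stronger readings might be inferred, and the documents do not support them.

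- A reader might infer that the baseline signals, the association with PASI change, the AUC or the power will be distorted. The documents give neither the share of patients using potent or unnamed topicals nor the size of any shift in signal, so no such effect can be claimed.
- A reader might infer that item 5 was meant to permit steroids up to moderate strength. That needs a word that is not in the text, and the finding does not depend on it.
- A reader might infer from the flow chart, which marks the inclusion/exclusion check at screening only, that eligibility lapses before baseline. Exclusion 1 already runs past screening ("or between the screening visit and drug initiation"), as does Exclusion 2 ("or between the screening and baseline visits"). Physical examination and concomitant medications are also scheduled at baseline. At most this is a matter of documentation, and it is not part of this point.

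**What to change.** Reword Exclusion 5 along these lines: *UVB therapy, or topical treatment of any kind except bland emollients (so including topical steroids of any strength), within 14 days before the baseline visit.*

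This brings the numbered list into line with the collection paragraph, removes the strength qualifier, covers classes not named, and ties the window to the visit at which the pre-treatment biopsies are taken. The cost is one reworded criterion. It needs no extra visit or procedure and adds no washout that the sponsor has not already stated. Topical use can be checked at the medication reviews already scheduled at screening and baseline.

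### Hepatitis B and C exposure is screened by history only; adding serology to the Screening labs would close the gap for unrecognised infection at little cost

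*Combined protocol and SAP*

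**What the plan says.** Exclusion item 18 excludes "Exposure to hepatitis B or hepatitis C or to high risk factors for hepatitis B or C, such as intravenous drug use in patient".

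The screening paragraph, which follows the adverse-event reporting text under Proposed experiments, says how eligibility is established: a TB test, skin and physical exams, and "medical history review, etc. as documented in the study flow sheet to determine if they meet the entrance requirements". The Flow Chart of visits is therefore the working list of procedures. Its only general laboratory row is "Screening labs (CBC, metabolic panel"), ticked at Screening and at no later visit. The other Screening entries are consent, medical history, concomitant medications, inclusion/exclusion review, TB test, urine pregnancy test, physical exam and the PASI/PGA/BSA/itch assessments.

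Other exclusions bear on the same patients. Item 2 excludes "Active or chronic infection within 4 weeks before screening visit, or between the screening and baseline visits". Item 16 excludes recent alcohol or drug abuse. Item 21 leaves room for clinical judgement.

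No hepatitis B or C assay is named anywhere. Blood taken from baseline onward is for PBMC isolation, and stored serum is for later cytokine and ANA measurement. Treatment is etanercept 50 mg twice weekly for 12 weeks.

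**The concern.** The protocol treats exposure to hepatitis B or C as a reason not to give etanercept. The scheduled means of finding it depend on what the patient knows and reports, plus non-specific signs. A patient who has an infection, does not know it, and reports no exposure or risk factor can meet every scheduled check and be treated to week 12. No hepatitis test and no repeat of the Screening labs is scheduled later.

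What is at stake is the protection of that patient against a risk the protocol has itself chosen to exclude. The analyses are not at stake.

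**Working it through.** **Step 1: which scheduled check could detect which patient.**

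| Scheduled check or criterion | What it can detect | Specific to hepatitis B or C? |
|---|---|---|
| Medical history, inclusion/exclusion review | Recognised exposure, reported risk factors | Only through what the patient reports |
| Physical exam | Visible signs, if any | No |
| CBC, metabolic panel | Abnormal values; the protocol names no panel components, threshold or reflex test | No |
| Item 2 (active or chronic infection) | Grounds to exclude; no test named | No |
| Item 16 (alcohol or drug abuse) | One reported risk factor | No |
| Item 21 (clinical judgement) | Grounds to exclude; no test named | No |
| TB test, urine pregnancy test | Other conditions | No |

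The group left uncovered is narrow: unrecognised infection, no reported exposure or risk factor, and nothing on the exam or panel that prompts further work-up.

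**Step 2: chance of enrolling such a patient (illustration).** The plan states no figure to reproduce. Inputs: n = 50 patients (Proposed experiments), and p, the share still infected among those who pass the existing screen. The documents do not give p, so it is assumed. Treating patients as independent:

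P(at least one) = 1 − (1 − p)^50

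| Assumed p | P(at least one of 50) | Expected number, 50p |
|---|---|---|
| 0.1% | 1 − 0.999^50 = 4.9% | 0.05 |
| 0.25% | 1 − 0.9975^50 = 11.8% | 0.125 |
| 0.5% | 1 − 0.995^50 = 22.2% | 0.25 |
| 1% | 1 − 0.99^50 = 39.5% | 0.5 |
| 2% | 1 − 0.98^50 = 63.6% | 1.0 |

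This is the chance of enrolment, not of harm.

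**Step 3: recruitment cost of testing.** Screen failures follow the test-positive rate q, which includes past exposure and false positives, so q is not the same as p. It is also assumed. To fill 50 places, 50/(1 − q) otherwise eligible patients must be tested, so

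extra failures = 50/(1 − q) − 50 = 50q/(1 − q)

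| Assumed q | Extra screen failures |
|---|---|
| 0.1% | 0.05/0.999 = 0.05 |
| 1% | 0.5/0.99 = 0.51 |
| 2% | 1.0/0.98 = 1.02 |
| 5% | 2.5/0.95 = 2.63 |

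If confirmatory testing returns some false positives to the trial, the number of failures is lower.

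**The case against.** The strongest case is that item 18 is a history criterion and already has its check. Exposure and risk factors such as intravenous drug use are ordinarily established by interview, and both the medical history and the inclusion/exclusion review are scheduled at Screening. This stands: item 18 can be applied as written. What history cannot do is find an infection the patient does not know about.

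A reader might infer something stronger: that the protocol implies testing and then fails to schedule it. Two comparisons invite this reading, and neither supports it.

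- *The missing qualifier.* Item 8 covers patients "known to have antibodies to etanercept" and item 14 covers "Known HIV-positive status or known history of any other immuno-suppressing disease", while item 18 has no such limit. But the protocol does not use the word consistently. Items 16, 19, 22 and 24 also lack it and have no specific test scheduled. Item 13 opens with known TB history, yet TB is the one infection that is tested.
- *The TB comparison.* Item 13 also refers to risk factors ("Any mycobacterial disease or high risk factors for tuberculosis (TB), such as family member with TB"), and the flow-chart footnote states "Subjects will be tested for TB at the screening visit". But item 13 names a positive skin-test result as an exclusion, so a test follows from its wording. Item 18 names no test result.

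It is also fair to object that every rate above is assumed, and that the documents do not describe what etanercept does in hepatitis B or C infection. Both points stand. They limit the priority of the suggestion but do not remove the reason for it, which is the protocol's own decision to exclude these patients.

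**Conclusion.** The point holds as an inexpensive patient-safety improvement of optional to moderate priority. The documents confirm that no hepatitis test is scheduled, that history and inclusion/exclusion review are the operative checks for item 18, and that a patient with unrecognised infection could be treated for 12 weeks.

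The documents do not support calling this an internal contradiction, and they support no statement about the number of patients affected or the harm to them. The 4.9% to 39.5% range rests entirely on an assumed 0.1% to 1% still infected after the present screen; 2% would give 63.6%. N = 50, the stated power and the planned analyses are unaffected.

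**What to change.** 1. In the Flow Chart of visits, add hepatitis B surface antigen, hepatitis B core antibody and hepatitis C antibody to the Screening labs row.
2. Require the results to be reviewed before drug is dispensed at BL. This needs its own sentence, because the inclusion/exclusion review is ticked only at Screening.
3. Do not dose a patient with a positive result. Exclude under item 18 and refer for clinical follow-up, unless confirmatory testing shows a false positive.

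Cost: an assay charge for each person screened. The documents give no prices, so calling it small is a judgement. There is also occasional staff time for informing a patient, confirmatory testing or referral, and the extra screen failures shown above, about 0.05 to 2.6 in filling 50 places if 0.1% to 5% test positive (assumed). The CBC and metabolic panel already need blood at Screening, and BL is a separate visit, so no new visit or invasive procedure is required.
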